5. HANDLING OF MISSING VALUES

Should missing data occur, the data will be analysed as they are recorded in the eCRFs, and no imputation of missing data will be performed.

All data analysis in this study will be performed on the Full Analysis Set containing all patients who fulfil the eligibility criteria, and thus missing data is not used as criteria for excluding the patients from the data analysis. However, due to the nature of the study, there will likely be missing data for data elements, ie, data that are not documented in the patient's medical record.

For both categorical and continuous variables, the amount of missing data will be reported. For categorical variables, the missing values will be analysed in the descriptive summary tables as a category. The missing values in the continuous variables will be ignored when calculating the summary statistics of mean, median, standard deviation and quantiles. If some of the variables of interest show to have a large amount or proportion of missing data, the summary statistics of the variable should be interpreted accordingly.

6. STATISTICAL METHODOLOGY AND STATISTICAL ANALYSES

This is a descriptive study, and as such, no statistical testing will be conducted. Summary statistics for patient demographics, clinical characteristics, treatment patterns and QoL will be performed. Summary statistics for continuous variables will include number of observations, mean, standard deviation, median, 1st and 3rd quartiles, minimum, and maximum. Summary statistics for categorical data will include number of observations, counts and percentages. Kaplan-Meier analyses will be performed on time-to-event outcomes, eg, TTP, response and death.

Analyses will be conducted using Statistical Analysis System (SAS, version 9.4 or higher) or R version 3.5 or higher.

6.1. Analysis for the Primary Objectives

Patients enrollment per country and site will be summarized as shown in [Table Shell 1](#).

For the primary objectives, clinical outcomes including the proportion of progression free and alive patients at different time intervals (6, 12, 18 and 24 months) and the proportion of patients who are alive 1 and 2 years post Palbociclib treatment initiation will be reported as shown in [Table Shell 2](#). The stratified tables will be presented as in Table Shells [3](#) - [9](#). The stratifications will be performed as described in [Section 3.2](#) by at least combination therapy and line of therapy.

The progression of the disease will be considered whenever the overall tumor response reported at any follow-up visit is progressive disease. The Kaplan-Meier (KM) method (product-limit method) will be used to estimate the proportion of subjects who are progression-free. The KM-estimate will be presented by 6 month intervals (6, 12, 18 and

24 months since the beginning of Palbociclib treatment) including the number of patients who were progression-free, those still at risk and the proportion of progression-free patients.

The proportion of the patients who are alive 1 and 2 years after Palbociclib treatment initiation will be calculated as the ratio of the number of patients who are alive 1 and 2 years over the number of patients who started the treatment (eligible patients).

6.2. Analysis for the Secondary Objectives

The objective response rate (ORR) will be described as shown in [Table Shell 2](#) and stratified in [Table Shells 3-9](#). The objective response will be defined as a state when either complete or partial response or stable disease has been reported as the overall tumor response in the last follow-up visit. ORR will be calculated as the ratio of the number of patients who are responsive to Palbociclib treatment (ie, have partial or complete response or stable disease for Palbociclib treatment recorded) over the number of patients who initiated Palbociclib treatment.³⁴ Censoring will be considered as described in [Section 3.1](#).

The demographic characteristics of the study population at breast cancer diagnosis for those receiving Palbociclib as first or second line therapy for metastatic/locally advanced BC will be described as shown in [Table Shells 10 and 11](#). Clinical characteristics of the study population at the initiation of Palbociclib treatment (baseline) those receiving Palbociclib as first or second line therapy will be described as shown in [Table Shells 12 and 13](#).

The dosing and dose changes, interruptions, delays and discontinuations associated with Palbociclib use in clinical practice will be described as shown in [Table Shell 14](#). The stratified tables will be presented as in [Table Shells 15 – 21](#).

The ten most common supportive therapies received by patients while receiving palbociclib combination treatment will be listed as shown in [Table Shell 22](#). The stratified tables will be presented as in [Table Shells 23 - 29](#).

The most common adjuvant therapies including systemic therapies, radiotherapy and surgeries will be described for early or locally advanced BC (stages 0-IIIa) patients as shown in [Table Shell 30](#). The stratified tables will be presented as in [Table Shells 31– 37](#).

The most common adjuvant therapies received by the advanced/metastatic BC patients (stages IIIB-IV) will be described both before and immediately after the first Palbociclib treatment as shown in [Table Shells 38 and 62](#), respectively. The stratified tables will be presented as in [Table Shells 39-45 and 63-69](#).

Quality of life of the patients receiving Palbociclib treatment at different follow-up visits will be described as shown in [Table Shell 47](#). The stratified tables will be presented as in [Table Shells 48-53](#). The EORTC quality of life questionnaire (QLQ-C30) will be used according to CRF. EORTC QLQ-30 scoring manual (version 3.0) will be used to group the items of the questionnaire into five functional scales, nine symptom scales, and a global health status, and to calculate scores for them. All of the scales and single-item measures range from 0 to 100;

a higher score represents a higher (“better”) level of functioning, or a higher (“worse”) level of symptoms. The procedure for scoring the scales is the same for all classes:

1. Estimate the average of the items that contribute to the scale; this is the raw scale.
2. Use a linear transformation to standardise the raw score so that scores range from 0 to 100.

Coding for SAS is provided in the appendix of EORTC QLQ-30 scoring manual.³⁵

Subgroup analyses will be performed as described in [Section 3.2](#).

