Clinical outcomes	
 Proportion of progression free survival/time to progression (at intervals per standard of care). Proportion of objective response rate (at intervals per standard of care). Complete response defined as complete reduction of all visible disease; partial response defined as partial reduction in size of visible disease in some or all areas without any areas of increase in visible disease; stable disease defined as no change in overall size of visible disease, also including cases where some lesions increased in size and some lesions decreased in size; progressive disease defined as an increase in visible disease and/or presence of any new lesions, including cases where the clinician indicates progressive disease. Time to response (at intervals per standard of care), defined as the time to first response among patients who achieved complete response or partial response. Proportion of overall survival (1- and 2-years post-treatment initiation). 	Patient records

Variable	Operational Definition	Data Source(s)
All lab investigations + other investigations	
 All lab investigation conducted including complete blood count (CBC). 	Patient records
Quality of life	
 To be assessed via EORTC QLQ-C30 (Cancer Quality of Life Questionnaire). 	Patient questionnaire

BC = breast cancer; CBC = complete blood count; ECOG = Eastern Cooperative Oncology Group; EORTC QLQ-C30 = European Organization for the Research and Treatment of Cancer Quality of Life Questionnaire Core 30; MBC = metastatic breast cancer.

Table 2. Data Entry Schedule

Data Collection and Entry ¹ ►	Baseline	During Treatment with Palbociclib	Post Treatment with Palbociclib
	SOC Visit ¹	SOC Follow-up visits ² through End of Treatment with Palbociclib	SOC Follow-up Visits through End of Study ³
Informed Consent & Inclusion/Exclusion Criteria	x		
Patient Demographics, Medical History, Baseline Metastatic Disease Status	x		
BC Diagnosis and Recurrence History	x		
Comorbid conditions	x	x	
Concomitant Medications	x	x	
BC Treatment ⁴	x	x	x ⁵
Performance Status (ECOG)	x	x	
Clinical Outcomes ⁶	x	x	
Laboratory investigations, including CBC ⁷	x	x	
EORTC QLQ-C30 ⁸	x	x	

BC = breast cancer; SOC = standard of care; CBC = complete blood count; ECOG = Eastern Cooperative Oncology Group; EORTC QLQ-C30 = European Organization for the Research and Treatment of Cancer Quality of Life Questionnaire Core 30.

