6.3. Analysis for the Exploratory Objectives

For the exploratory analyses, time to response (TTR), time to progression (TTP)/ progression free survival (PFS) will be studied and results will be presented as shown in [Table Shell 54](#). The stratified tables will be presented as in Table Shells [55-61](#).

TTR is defined as the length of time (in days) from the initiation of Palbociclib treatment until the first reported disease response (complete or partial).³⁴ Censoring rules presented in [Section 3.1](#) will be applied.

TTP is defined as the length of time (in days) from the initiation of Palbociclib treatment until the first reported disease progression.³⁴ Patients will be censored at the end of Palbociclib treatment, death, time of withdrawal, or end of the 24-month follow-up, whichever occurs first, at the respective time point. Specifically, death is not included in TTP but is considered as censoring event.

PFS is defined as the length of time (in days) from the initiation of Palbociclib treatment until the first reported disease progression or death due to any cause, whichever occurs first.³⁴ The disease progression will be considered at the first follow-up visit after the Palbociclib treatment initiation when the overall tumor response recorded is progressive disease. Patients with no disease progression documented will be censored at the last available medical record entry or end of the follow-up period. Patients who are lost to follow-up will be censored at their last visit.

Survival analyses will be used to estimate time to event endpoints TTR, TTP and PFS. The results of the survival analysis will be presented as the Kaplan-Meier survival curves and their 95% confidence intervals (CIs) that will be calculated using the log-log transformation of the survival probabilities.³⁶ Together with the Kaplan-Meier plots, the number of patients at risk at time intervals (eg, 90 days or as seen appropriate for the study) will be reported. [Figure Shells 1 and 2](#) show how time to response (TTR) and progression free survival (PFS) will be visualized as Kaplan-Meier plots including the number of patients at different time intervals. Kaplan-Meier plots can be presented by other categories (see [Section 3.2](#)), if enough data are available. Moreover, the results of the survival analysis will be reported as a descriptive summary table including the number of patients at risk, the number of patients

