Number of patients with lesions	Clinical characteristics (secondary endpoint)	At diagnosis of advanced/metastatic BC	CRF sheet: Palbociclib Baseline Tumor Assessment	
Number of patients with lesions according to site. Sites of lesions are categorized as:
 
 Brain (visceral) Lung/pleura (visceral) Liver (visceral) Bone (non-visceral/bone-only) Breast/chest wall (non-visceral) Lymph nodes (none) Skin/soft tissue (non-visceral) Ovary (non-visceral) Other (e.g. peritoneal (visceral))
ECOG performance	Clinical characteristics (secondary endpoint)	At diagnosis of advanced/metastatic BC	CRF sheet: Palbociclib Baseline Tumor Assessment	
ECOG status will be categorised as
 
 0: Fully active, able to carry on all pre-disease performance without restriction 1: Restricted in physically strenuous activity but ambulatory and able to carry out work of a light or sedentary nature, e.g. light housework, office work 2: Ambulatory and capable of all self-care but unable to carry out any work activities. Up and about 50% of waking hours 3: Capable of only limited self-care, confined to bed or chair more than 50% of waking hours 4: Completely disabled, cannot carry on any self-care. Totally confined to bed or chair. 5: Dead

PFIZER CONFIDENTIAL

CT24-WI-GL03-RF02 2.0 Non-Interventional Statistical Analysis Plan For Primary Data Collection Study 01-Jun-2020

Variable	Role	Time point(s)	Data source(s)	Operational definition
Overall tumor response	Clinical outcomes (primary endpoint)	At follow-up visits	CRF sheet: Tumor Assessment form	
Overall tumor response will be categorised as:
 
 Progressive disease, defined as an increase in visible disease and/Or presence of any new lesions, including cases where the clinician indicates progressive disease Complete response, defined as complete reduction of all visible disease Partial response, defined as partial reduction in size of visible disease in some or all areas without any areas of increase in visible disease Stable disease, defined as no change in overall size of visible disease, also including cases where some lesions increased in size and some lesions decreased in size

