CT24-WI-GL03-RF02 2.0 Non-Interventional Statistical Analysis Plan For Primary Data Collection Study 01-Jun-2020

Page 43 of 172

0901776099673e30A5481150 Palbociclib Read On: 28-Mar-2023 09:56 (GMT)

Variable	Role	Time point(s)	Data source(s)	Operational definition
Time to progression (TTP)	Clinical outcomes (exploratory endpoint)	At the follow-up visits	CRF sheet: Tumor Assessment Form and End of follow-up	The time from the first breast cancer diagnosis to the first reported progression of the disease or death from the disease, whichever occurs first.
Objective response rate (ORR)	Clinical outcomes (secondary endpoint)	At the follow-up visits	CRF sheet: Tumor Assessment Form	The proportion of the patients who have been reported to be responsive (partial or complete response or stable disease) for the treatment.
Time to first response	Clinical outcomes (exploratory endpoint)	At the follow-up visits	CRF sheet: Tumor Assessment Form	The time from the first breast cancer diagnosis to the first reported response (partial or complete response) for the treatment.
Proportion of overall survival	Clinical outcomes (primary endpoint)	At 1 and 2 years after the treatment initiation	CRF sheet: Tumor Assessment Form and End of follow-up	The proportion of alive patients over all patients who initiated the treatment.
Item	Quality of life (secondary endpoint)	At follow-up visits	CRF sheet: Patient reported outcomes (PROs)	There are 28 questions (items) in EORTC-QLQ-30 questionnaire that are classified as follows: 1: Not at all 2: A little 3: Quite a bit 4: Very much
Item	Quality of life (secondary endpoint)	At follow-up visits	CRF sheet: Patient reported outcomes (PROs)	There are 4 questions (items) in EORTC-QLQ-30 questionnaire that are classified as follows: 1 (Very Poor) - 7 (Excellent)

BC=breast cancer; CBC=complete blood count; ECOG=Eastern Cooperative Oncology Group; EORTC QLQ-C30=European Organization for the Research and Treatment of Cancer Quality of Life Questionnaire Core 30; MBC=metastatic breast cancer.

10. ANNEX 2

Table Shell 1 – Summary of patients enrollment per country and site.

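### The figure SAP 6.2 labels ORR is the share of initiators whose last recorded assessment is not progression, whereas response elsewhere in the plan means CR or PR

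*SAP*

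**What the plan says.** SAP 6.2 defines objective response as the state in which "either complete or partial response or stable disease has been reported as the overall tumor response in the last follow-up visit". Its next sentence gives the rate without naming a visit: patients who "have partial or complete response or stable disease for Palbociclib treatment recorded", divided "over the number of patients who initiated Palbociclib treatment". SAP Annex 1, Table 3 likewise counts patients who "have been reported to be responsive (partial or complete response or stable disease) for the treatment", again with no visit named. Table Shells 2 to 9 print PD, CR, PR, SD and missing under a heading that ties tumour response to the close of palbociclib therapy, with ORR underneath.

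Annex 1 has four response categories. One of them is "Stable disease, defined as no change in overall size of visible disease, also including cases where some lesions increased in size and some lesions decreased".

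Elsewhere response is narrower. Protocol 8.3, Table 1 has time to response (TTR) "defined as the time to first response among patients who achieved complete response or partial response". SAP 6.3 measures TTR from the start of palbociclib "until the first reported disease response (complete or partial", and SD does not appear there.

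**The concern.** Two features of the ORR rule depart from what the label tells a reader. SD counts as response, and status is taken at the last visit instead of as best response. ORR is the first-listed secondary objective, is stratified in Table Shells 3 to 9, and the results are intended for publication. A reader will take ORR to mean CR+PR and compare it with the best-response figures in the background sections. In the same output set, the patients counted as responders for ORR will not be those with a response event for TTR. Because 6.2 and Annex 1 differ on timing, two programmers could also follow the SAP faithfully and report different ORRs.

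**Working it through.** The documents give no target, assumed value or precision for ORR, so there is no plan figure to reproduce. The check is one of logic, followed by an illustration from figures the documents cite.

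**Logic.** Every initiator is PD, CR, PR, SD or missing at the last assessment, so

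SAP ORR = (CR + PR + SD) / initiators = 1 − PD − missing.

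| Patient | SAP 6.2, last visit | 6.2 / Annex 1, ever recorded | CR or PR at any time (TTR event) |
|---|---|---|---|
| PR, maintained | yes | yes | yes |
| PR, later PD | **no** | yes | yes |
| SD only, then lost, withdrawn or stopped without PD | **yes** | **yes** | no |
| SD only, dies without recorded PD | **yes** | **yes** | no |
| PD at first assessment | no | no | no |
| Never assessed | no | no | no |

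Bold marks disagreement with the last column. Since SD already scores 1, a later CR or PR adds nothing. The only change open to an assessed patient is from 1 to 0 at PD, and SAP 3.1 ends follow-up there. Among assessed patients the rate can therefore only hold or fall. Over all initiators it can rise briefly while first assessments arrive.

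**Benchmark.** The database study cited in protocol 6.1 and SAP 2 reports best response for palbociclib plus aromatase inhibitor: CR 9.5% + PR 50.5% = 60.0%, or 120 of 200.

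**Illustration 1.** Approximate the last-visit rule by the progression-free rates cited for first-line palbociclib plus letrozole (US chart review, a different cohort from the benchmark).

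| Month | Approximate SAP ORR | Of 200 | Minus 60.0% |
|---|---|---|---|
| 6 | 92.7% | 185 | +32.7 points |
| 12 | 75.5% | 151 | +15.5 points |
| 18 | 51.6% | 103 | −8.4 points |

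Log-linear interpolation puts the crossing at 12 + 6 × (ln 0.600 − ln 0.755) / (ln 0.516 − ln 0.755) ≈ 15.6 months.

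**Illustration 2.** Take exponential progression with the cited trial medians, λ = ln 2 / median. Assume a fraction d stop without PD by month 24 and keep a non-PD last status, μ = −ln(1 − d) / 24. Then

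rate(t) = 1 − [λ / (λ + μ)] × (1 − exp(−(λ + μ)t)).

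| Median PFS | d (assumed) | 12 months | 24 months |
|---|---|---|---|
| 24.8 months (with letrozole) | 0 | 71.5% | 51.1% |
| 24.8 months | 30% | 73.8% | 58.1% |
| 9.5 months (with fulvestrant) | 0 | 41.7% | 17.4% |
| 9.5 months | 30% | 45.9% | 27.0% |

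With d = 0 the formula reduces to 0.5^(t/median); for example 0.5^(24/24.8) = 0.511.

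**Ever-recorded reading.** With CR+PR at 60.0%, counting SD as well gives anything from 60.0% to 100%, depending on how many patients have SD as their best response. That is a disease control rate. It does not fall with follow-up, but it is not CR+PR.

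**The case against.** The strongest reply is that the information survives. The shells print CR, PR, SD, PD and missing beside ORR, and Table Shell 54 counts patients with a TTR event, which is close to the number ever reaching CR or PR. Most of this stands as mitigation. It is partial, because the CR and PR rows in Table Shells 2 to 9 show status at the end of treatment, so best response cannot be read from them, and the line called ORR would still disagree with the TTR count.

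Four stronger readings are tempting, and the documents do not support them.

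- *ORR simply duplicates PFS, or is the complement of PD.* Unassessed patients stay in the denominator, and deaths, losses and stops without recorded PD keep a non-PD status. The illustrations are approximations.
- *The rate falls from about 80% to 17%.* That would splice 12-month real-world rates onto a 24-month curve from a fulvestrant trial in women who had relapsed or progressed on endocrine therapy. Within one curve the fall is 71.5% to 51.1%, or 41.7% to 17.4%.
- *The value drifts without limit.* Follow-up is capped at 24 months. Protocol section 5 allows data collection from 15 July 2021 to 30 April 2025, which is longer than 18 + 24 = 42 months, so unequal potential follow-up matters mainly at the interim report. A best-response ORR also depends on follow-up, though it can only rise.
- *The SAP breaks an explicit protocol definition.* The protocol never states that ORR is CR+PR; that meaning comes from its TTR definition. Protocol 8.7 also lets the SAP modify planned analyses. The outside source that 6.2 cites for its definition was not available to check.

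**Conclusion.** The point holds as a definitional inconsistency. SAP 6.2 puts under the label ORR the proportion of initiators whose last recorded assessment is not PD. Its alternative wording gives a disease control rate. Neither matches the CR/PR meaning of response in protocol Table 1 and SAP 6.3.

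The direction of the error depends on follow-up: in the letrozole illustration, from about 33 points above the 60.0% benchmark at 6 months to about 8 points below it at 18. Those sizes assume that progression-free rates approximate the last-visit rule, and they compare different cohorts. The logical result, that the rate cannot rise once patients have been assessed, needs neither assumption.

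ORR is secondary, nothing is tested, and no primary endpoint or sample size is affected. With the partial mitigation in the shells, this should be fixed, but it does not undermine the study.

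**What to change.** In SAP 6.2, Annex 1 (Table 3) and Table Shells 2 to 9:

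- Define ORR as the proportion of all patients initiating palbociclib whose best overall response is CR or PR at any post-baseline assessment up to the earliest of progression, end of palbociclib treatment or month 24. This matches SAP 3.1 censoring. The window should not extend past end of treatment, because the data entry schedules (protocol Table 2, SAP Table 1) mark clinical outcomes only at baseline and during treatment.
- Keep unassessed patients in the denominator and show their number.
- Report best response by category, and ORR with a 95% CI. At 60% and N = 200 the half-width is 1.96 × √(0.6 × 0.4 / 200) ≈ 6.8 points.
- Change the shell heading from end-of-treatment response to best response.
- If CR+PR+SD is wanted, report it separately as disease control rate.

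The cost is SAP wording and relabelled shells. On-treatment visit-level responses are already collected on the tumour assessment form. Protocol 8.7 reserves amendments for major changes to primary endpoints, so none is needed. Comparison with the cited benchmark would remain approximate, since that study counted only responses at least 30 days after initiation.
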